- j. Participants must have absence of signs of cirrhosis or portal hypertension (absence of nodules, smooth liver contour, normal portal vein, spleen size <12 cm) and absence of signs of HCC or clinically relevant renal abnormalities on an abdominal ultrasound performed within 3 months prior to screening or at the time of screening. In case of suspicious findings on conventional ultrasound the participant may still be eligible if HCC or clinically relevant renal abnormalities have been ruled out by a more specific imaging procedure (contrast-enhanced ultrasound, CT or MRI).
- k. HBV genotype will be determined at baseline using a standard genotyping assay if HBV DNA levels are sufficiently high. Available historical data on a previous HBV genotype assessment will also be collected in the CRF. Exploratory genotyping may be performed.
- l. Not applicable for the WD visit.
- m. In between study visits, participants will take NA at home and will bring their NA with them to each study visit. At study visits, NA should be taken on site. Weekly PegIFN- α 2a administration should preferably be done on the same day of the week in the evening by self-injection. A total of 12 injections should be administered, starting at Week 12, with the last injection during Week 23. If desired, participants can also choose to have the weekly administration of PegIFN- α 2a performed on site irrespective of the time of day. For participants in Japan, weekly administration of PegIFN- α 2a must be performed at the study site by the investigator or his/her designee.
- n. Only applicable in case of self-injection.

- o. Participants who are administering PegIFN- α 2a by self-injection will be requested to complete a self-injection tracker. Refer to Section 6.4, Study Intervention Compliance, for more details.
- p. Complete physical examination, including height (only at screening), body weight, skin examination, and other body systems.
- q. For participants with a risk factor (eg, diabetes or hypertension), an ophthalmic examination should be repeated at Week 8 (+/- 3 weeks) at the investigator's discretion in case their condition changes. Any participant experiencing a decrease or loss of vision at any time point during study participation, must have a prompt ophthalmic examination. Medical records of the examination should be collected and assessed by the investigator.
- r. A +/- 3-week visit window is allowed for the ophthalmic examination at Week 24.

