2.2.3.3. Combination of JNJ-3989 and JNJ-6379 with PegIFN- α 2a

PegIFN- α 2a is a covalent conjugate of recombinant alfa-2a interferon that is indicated for the treatment of CHB in adult and pediatric patients at least 3 years of age. In addition, PegIFN- α 2a in combination with other medicinal products is indicated for the treatment of chronic hepatitis C virus (HCV)-infection in adult and pediatric patients at least 5 years of age and not treated before. The most common adverse reactions ($\geq 10\%$ of participants) are anorexia, anxiety, headache, concentration impairment, dyspnea, cough, alopecia, dermatitis, pruritis, dry skin, myalgia, arthralgia, asthenia, pyrexia, and fatigue. For further information regarding PegIFN- α 2a, refer to the currently approved prescribing information.

Treatment with PegIFN- α 2a has been associated with decreases in platelet count (common adverse reaction). In the Phase 1/2a AROHBV1001 study (see Section 2.2.3.1, JNJ-3989 and JNJ-6379), no effect on platelet count has been observed in the triple combination treatment cohort 12 (JNJ-3989, JNJ-6379, and NA). Of the 84 adult chronic HBV-infected participants that received 3 subcutaneous injections of JNJ-3989, 6 participants developed grade 1 platelet reduction with no general trend towards a continuous decline. For JNJ-6379, no effect on platelet count has been observed in ongoing Phase 2a 56136379HPB2001 study (JADE) for the 189 adult chronic HBV-infected participants that were dosed with JNJ-6379.

Based on pre-clinical data, a potential common toxicity target organ between JNJ-6379, JNJ-3989, and PegIFN- α 2a is the bone marrow (see Section 2.2.2, Nonclinical Studies). Bone marrow suppression is a known side effect of PegIFN- α 2a (rare).

No PK interaction is expected between JNJ-3989 or JNJ-6379 and PegIFN- α 2a based on the known pharmacologic profile of the compounds (IB JNJ-3989 2020; IB JNJ-6379 2021; Yeh 2019).

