- Any investigational agent, investigational vaccine, invasive investigational medical device, or investigational biological product (other than the study intervention taken in the context of this study).
Note: Approved COVID-19 vaccines or COVID-19 vaccines with conditional marketing authorization, emergency use authorization or special approval for emergency are allowed.

Disallowed from 6 months prior to baseline until end of follow-up:

- Any systemically (eg, intravenously, intramuscularly, orally, subcutaneously) administered medication that directly or indirectly interferes with immune responses (eg, cyclosporine, interleukins, systemic corticosteroids exceeding 5 mg of prednisolone equivalent/day).

Disallowed from screening until end of follow-up:

- Any anti-HBV drug (including vaccines) other than the study intervention taken in the context of this study.
Note: NA standard of care treatment is allowed between screening and baseline.
- Biotin (>1 mg daily dose), either taken alone or as part of a multivitamin formulation.
Note: The use of other vitamins is allowed.
- Topical steroids (>7 days) under occlusive dressing.

Note: The list of disallowed concomitant medication is not exhaustive; for products falling in one of the categories and not mentioned by name, the sponsor should be contacted to determine whether the product can be allowed.

The prescribing information for ETV, tenofovir disoproxil, TAF, and PegIFN- α 2a should be consulted for any additional prohibited medication. In case of flu-like symptoms after administration of PegIFN- α 2a, paracetamol up to a maximum of 2 g per 24 hours and a maximum of 6 g per week is allowed.

Medications requiring subcutaneous injection (other than JNJ-3989 and PegIFN- α 2a; eg, insulin) should be administered away from the JNJ-3989 and PegIFN- α 2a injection sites.

6.6. Study Intervention Completion at Week 24

With the implementation of Protocol Amendment 3, all participants had to stop JNJ-6379 treatment immediately.

Participants will stop treatment with JNJ-3989 and PegIFN- α 2a at Week 24 (EOSI). If all of the following NA treatment completion criteria are met at Week 24, treatment with NA will also be stopped at the next scheduled visit (ie, FU Week 2):

- The participant has ALT $<3x$ ULN, AND
- The participant has HBV DNA $<LLOQ$, AND
- The participant is HBeAg-negative, AND
- The participant has HBsAg <10 IU/mL.

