7.1. Discontinuation of Study Intervention

With the implementation of Protocol Amendment 3, all participants had to stop JNJ-6379 treatment immediately.

Treatment with JNJ-3989 (and PegIFN- α 2a during Treatment Period 2) must be discontinued before Week24/EOSI if any of the discontinuation criteria listed below are met. Criteria specific for this ISA are highlighted (colored fill). For the few criteria from the Master Protocol that are specified or more restricted in this ISA, the changes compared to the Master Protocol are also highlighted (colored fill). If JNJ-3989 is discontinued, PegIFN- α 2a (only applicable in Treatment Period 2) should also be discontinued. NA treatment may be continued or, in consultation with the sponsor, discontinued based on investigator judgement.

The discontinuation criteria are:

- The participant withdraws consent to receive study intervention.
- The investigator believes that for safety or tolerability reasons (eg, AE) it is in the best interest of the participant to discontinue JNJ-3989 (and PegIFN- α 2a, if applicable).
- The participant becomes pregnant.
- The participant has a \geq grade 3 rash (see Section 10.6, Appendix 6: Rash Management) or allergic reaction (see Section 8.3.6.3, Acute Systemic Allergic Reactions).
- The participant has signs of hepatic decompensation (ie, clinical evidence of ascites, bleeding varices, or hepatic encephalopathy) or an increase in direct bilirubin $>1.5x$ ULN in combination with INR $\geq 1.5x$ ULN or albumin <3.0 g/dL, treatment with JNJ-3989 should be discontinued and alternative treatment options (outside the study) should be considered in discussion with the sponsor.
- The participant has a confirmed \geq grade 3 eGFR abnormality, considered at least possibly related to JNJ-3989 (or PegIFN- α 2a, if applicable) that persists despite change of tenofovir disoproxil to ETV or TAF (if the patient was receiving tenofovir disoproxil). Change of NA treatment should be considered according to the prescribing information (see Section 8.3.6.5, Renal Complications).
- The participant has a QTcF prolongation (defined as a QTcF value of >500 ms, or an increase from baseline of >60 ms) at any given time point.
- The participant requires ≥ 7 days of treatment with any of the disallowed medications listed in Section 6.5, Concomitant Therapy, and does not intend to discontinue treatment with the disallowed medication.

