Definition	Study Intervention Action	Activities by Day ^a	Referral to Dermatologist and Dermatology Activities
		
higher grade, safety laboratory assessments of the higher grade should be followed.
 
Digital pictures^c of skin lesions may be taken at the investigator’s discretion.
	

Grade 3 rash^b
 
Vesiculation, moist desquamation, or ulceration OR
 
Any cutaneous event with 1 of the following:
 
 - Elevations in AST/ALT >2×baseline value - Fever >38°C or 100°F - Eosinophils >1.00×10³/μL - Serum sickness-like reaction 	
Must permanently discontinue JNJ-3989 and PegIFN-α2a; no rechallenge allowed
 
NA treatment may be discontinued based on investigator judgement in consultation with the sponsor
	
Day 0: required on-site visit.
 
Safety laboratory assessments required to be performed.
 
Digital pictures^c of skin lesions may be taken at the investigator’s discretion (recommended).
 
Determine if participant was adhering to the recommended sun-protective measures. If appropriate, provide sun protection counseling.
 
Day 1: required on-site visit.
 
Safety laboratory assessments required to be performed.
 
Digital pictures^c of skin lesions may be taken at the investigator’s discretion (recommended).
 
Further visit(s): appropriate follow-up required until resolution of rash or until clinical stability is reached.
 
Safety laboratory assessments and photography (digital pictures^c of skin lesions) are recommended to be performed until the rash severity resolves to grade 2 or grade 1.
	
Required^d
 
Biopsy not required, but may be performed at the dermatologist’s discretion.

Table 5: Management of Rash Events by Severity Grade

	Definition	Study Intervention Action	Activities by Day^a	Referral to Dermatologist and Dermatology Activities

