Visual Changes (assessed from baseline)	Visual changes causing no or minimal interference with usual social & functional activities	Visual changes causing greater than minimal interference with usual social & functional activities	Visual changes causing inability to perform usual social & functional activities	Disabling visual loss in affected eye(s)

dB: decibel; kHz: kilohertz; NAP: not applicable

PARAMETER	SYSTEMIC			
	GRADE 1 MILD	GRADE 2 MODERATE	GRADE 3 SEVERE	GRADE 4 POTENTIALLY LIFE- THREATENING
Acute Allergic Reaction	Localized urticaria (wheals) with no medical intervention indicated	Localized urticaria with intervention indicated OR Mild angioedema with no intervention indicated	Generalized urticaria OR Angioedema with intervention indicated OR Symptoms of mild bronchospasm	Acute anaphylaxis OR Life-threatening bronchospasm OR Laryngeal edema
Chills	Symptoms causing no or minimal interference with usual social & functional activities	Symptoms causing greater than minimal interference with usual social & functional activities	Symptoms causing inability to perform usual social & functional activities	NAP
Cytokine Release Syndrome^h	Mild signs and symptoms AND Therapy (ie, antibody infusion) interruption not indicated	Therapy (ie, antibody infusion) interruption indicated AND Responds promptly to symptomatic treatment OR Prophylactic medications indicated for ≤ 24 hours	Prolonged severe signs and symptoms OR Recurrence of symptoms following initial improvement	Life-threatening consequences (eg, requiring pressor or ventilator support)
Fatigue or Malaise Report only 1	Symptoms causing no or minimal interference with usual social & functional activities	Symptoms causing greater than minimal interference with usual social & functional activities	Symptoms causing inability to perform usual social & functional activities	Incapacitating symptoms of fatigue or malaise causing inability to perform basic self-care functions
Fever (non-axillary temperatures only)	38.0°C to <38.6°C or 100.4°F to <101.5°F	$\geq 38.6^\circ\text{C}$ to <39.3°C or $\geq 101.5^\circ\text{F}$ to <102.7°F	$\geq 39.3^\circ\text{C}$ to <40.0°C or $\geq 102.7^\circ\text{F}$ to <104.0°F	$\geq 40.0^\circ\text{C}$ or $\geq 104.0^\circ\text{F}$

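### Rash Table 5 gives two non-equivalent fever limits (38°C and 100°F) in a rule that permanently stops JNJ-3989 and PegIFN-α2a; wrong as written, minor

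*Protocol*

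**What the plan says.** Protocol Appendix 6, Table 5, defines Grade 3 rash in two ways. The first is by skin morphology. The second is "Any cutaneous event with 1 of the following", followed by four features: an AST/ALT rise, a fever limit, an eosinophil count and a serum-sickness-like reaction. The fever limit is "Fever >38°C or 100°F".

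The action for Grade 3 is "Must permanently discontinue JNJ-3989 and PegIFN-α2a; no rechallenge allowed". On-site visits on Day 0 and Day 1 and referral to a dermatologist are also required. For Grade 1 (erythema), dosing may continue at the investigator's discretion, the visit is optional and no referral is needed.

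Section 7.1 lists rash of this grade or worse among the criteria for mandatory discontinuation and points back to the same table: "grade 3 rash (see Section 10.6, Appendix 6: Rash Management". It adds that stopping JNJ-3989 also means stopping PegIFN-α2a.

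The DAIDS table in Appendix 9 has its own fever row. Its Grade 1 band is "38.0°C to <38.6°C or 100.4°F to <101.5°F".

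**The concern.** A stopping rule should give one answer for one reading. Here the line holds two numbers that look like one limit in two units, but they are 0.4°F apart. A reading between them meets one and not the other, and no section says which governs or that 100°F is a rounded value.

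At stake is the permanent loss of both agents in a participant whose rash would otherwise be Grade 1 or 2, where treatment may continue. The combination of a skin reaction and a slightly raised temperature is plausible once PegIFN-α2a starts. Section 2.2.3.3 includes "dermatitis, pruritis, dry skin, myalgia, arthralgia, asthenia, pyrexia, and fatigue" in its list of reactions seen in at least 10% of participants. Section 6.5 allows paracetamol "In case of flu-like symptoms after administration of" PegIFN-α2a.

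**Working it through.** **Inputs.** The Table 5 pair (38°C, 100°F); the four lower limits of the Appendix 9 fever row; the dosing days in the Schedule of Activities (Section 1.3).

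**1. Does the Table 5 pair convert?**
- °F = °C × 9/5 + 32: 38 × 9/5 + 32 = 100.4°F, not 100°F.
- °C = (°F − 32) × 5/9: (100 − 32) × 5/9 = 37.78°C, not 38°C.
- Gap: 100.4 − 100 = 0.4°F, or 38 − 37.78 = 0.22°C.

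**2. Does the protocol convert correctly elsewhere?** The same formula applied to the Appendix 9 fever row:

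| Printed °C | Computed °F | Printed °F |
|---|---|---|
| 38.0 | 100.40 | 100.4 |
| 38.6 | 101.48 | 101.5 |
| 39.3 | 102.74 | 102.7 |
| 40.0 | 104.00 | 104.0 |

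All four pairs agree to within 0.05°F. The mismatch is specific to Table 5.

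**3. Which readings change class?** The greater-than sign is taken to apply to both figures.

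| Reading °C | In °F | Above 38°C? | Above 100°F? |
|---|---|---|---|
| 37.7 | 99.86 | no | no |
| 37.8 | 100.04 | no | yes |
| 37.9 | 100.22 | no | yes |
| 38.0 | 100.40 | no | yes |
| 38.1 | 100.58 | yes | yes |

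Three one-decimal Celsius readings fall between the limits. In Fahrenheit the readings are 100.1, 100.2, 100.3 and 100.4 (37.83, 37.89, 37.94 and 38.00°C). Every reading above 38°C is also above 100°F, so under the literal wording the Celsius figure does no work. Of the three Celsius readings, 37.8 and 37.9 lie below the start of Grade 1 fever in Appendix 9; 38.0 lies on it.

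**4. What does a stop cost in doses?** JNJ-3989 is given on Day 1 and at Weeks 4, 8, 12, 16 and 20, which is 6 injections. For PegIFN-α2a, footnote m of the schedule says "A total of 12 injections should be administered, starting at Week 12, with the last injection during Week 23".

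| Stop after | JNJ-3989 forgone | PegIFN-α2a forgone |
|---|---|---|
| Day 1 dose | 6 − 1 = 5 of 6 | 12 of 12 |
| First PegIFN-α2a dose, Week 12 | 6 − 4 = 2 of 6 | 12 − 1 = 11 of 12 |

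The rash rule applies from Day 1, so the first row is the larger loss. A stop later than Week 12 costs less than the second row.

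**The case against.** The strongest reply is that the line is not ambiguous. The two figures are joined by *or*, so exceeding either is enough: 37.9°C is 100.22°F and qualifies in whichever unit it was written down. The general instructions in Appendix 9 point the same way, since they tell sites to choose the higher grade when an event could fall under two. On that reading there is one limit, about 37.8°C, and it is the cautious one.

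Part of this stands. A reader might infer that the recorded unit alone decides whether treatment stops. The documents do not support that, because the literal wording gives the same answer in both units. Divergence arises only if a site treats the pair as one limit in two units and works from its own. That is a natural reading, because the figures are printed like a conversion and 38°C would otherwise have no function. Whether the higher-grade instruction governs Table 5 is arguable, because the table has its own rash definitions.

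A second reply is that sites probably work in Celsius. SAP Section 5.6.3.4 analyses body temperature in °C, SAP Table 11 lists Poland, Taiwan, Japan and New Zealand, and nothing shows a site recording °F. This makes it likely that many sites apply 38°C. It does not remove the second number from the line they read.

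A third is that Section 8.3.6.1 allows standard management of rash. That covers rash most likely due to concomitant illness or non-study treatment. PegIFN-α2a is a study intervention, so a rash attributed to it gets no relief.

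Finally, a rash rule may legitimately act below the Grade 1 fever threshold. That is fair: Appendix 9 is evidence about the conversion, not about where the rash limit ought to lie.

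**Conclusion.** Wrong as written, minor: an internal inconsistency in a stopping threshold. The limits differ by 0.4°F (0.22°C), and the same line can support opposite mandatory actions at 37.8, 37.9 and 38.0°C when the rash is otherwise mild and no other Grade 3 feature is present.

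The conclusion assumes that the greater-than sign covers both figures. If 100°F were instead inclusive, the one-decimal Celsius list would not change, since 37.7°C is 99.86°F. Rounding of 100.4°F is the likely origin, but the protocol does not say so.

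Two stronger inferences are not supported. One is that the loss from a Week 12 stop (11 of 12 and 2 of 6 injections) is the worst case; a stop after the Day 1 dose forgoes more. The other is that the slip would distort the trial's results. The sample size, primary endpoint definition and analysis sets do not use this limit. Dermatitis and pyrexia are listed separately, with no rate for their joint occurrence or for readings in this band, so the number affected cannot be estimated.

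**What to change.** In Table 5, print the Grade 3 fever feature as *Fever >38.0°C (>100.4°F)*. This keeps the Celsius limit and uses the conversion already in Appendix 9. If the sponsor does want the lower limit, the line should say so in both units, as >37.8°C with its Fahrenheit equivalent.

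The cost is one figure, corrected at the next amendment or by letter to sites. No assessment, visit or analysis is added.

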10.7. Appendix 7: Intervention-emergent ALT/AST Elevations

^a Additional tests may be considered based on clinical judgement in case of confirmed ALT flares:

- Hepatitis A, Delta, C, E: IgM anti-HAV; delta IgM, IgG and PCR, HCV RNA, IgM and IgG anti-HEV, HEV RNA
- CMV, HSV, EBV infection: IgM and IgG anti-CMV, IgM and IgG anti-HSV; IgM and IgG anti-EBV, PCR
- HIV
- Ig-Electrophoresis

10.8. Appendix 8: Cardiovascular Safety – Abnormalities**ECG**

All important abnormalities from the ECG readings will be listed.

Abnormality Code	ECG parameter			
	Heart Rate	PR	QRS	QT _{corrected}
Abnormalities on actual values				
Abnormally low	<45 bpm	NAP	-	-
Abnormally high	≥120 bpm	>220 ms	≥120 ms	-
Borderline prolonged QT	-	-	-	450 ms < QTc ≤480 ms
Prolonged QT	-	-	-	480 ms < QTc ≤500 ms
Pathologically prolonged QT	-	-	-	QTc >500 ms
Abnormalities on changes from baseline (ΔQTc)				
Normal QTc change	-	-	-	ΔQTc <30 ms
Borderline QTc change	-	-	-	30 ms ≤ ΔQTc ≤60 ms
Abnormally high QTc change	-	-	-	ΔQTc >60 ms

ECG: electrocardiogram; NAP = not applicable

For absolute QTc parameters the categories are defined based on the International Council for Harmonisation of Technical Requirements for Pharmaceuticals for Human Use (ICH) E14 Guidance^a

Vital Signs^b

The following abnormalities will be defined for vital signs:

Abnormality Code	Vital Signs parameter		
	Pulse	DBP	SBP
Abnormalities on actual values			
Abnormally low	≤45 bpm	≤50 mmHg	≤90 mmHg
Grade 1 or mild	-	>90 mmHg - <100 mmHg	>140 mmHg - <160 mmHg
Grade 2 or moderate	-	≥100 mmHg - <110 mmHg	≥160 mmHg - <180 mmHg
Grade 3 or severe	-	≥110 mmHg	≥180 mmHg
Abnormally high	≥120 bpm	-	-

DBP: diastolic blood pressure; SBP: systolic blood pressure

^a The clinical evaluation of QT/QTc interval prolongation and proarrhythmic potential for non-antiarrhythmic drugs CHMP/ICH/2/04, May 2005.

^b The classification of AEs related to hypotension and hypertension will be done according to the DAIDS grading scale.

10.9. Appendix 9: DAIDS Table**DIVISION OF AIDS (DAIDS) TABLE FOR GRADING THE SEVERITY OF ADULT AND PEDIATRIC ADVERSE EVENTS, VERSION 2.1, PUBLISH DATE: JULY, 2017**

The DAIDS grading table is a descriptive terminology to be utilized for AE reporting in this study. A grading (severity) scale is provided for each AE term.

General Instructions***Grading Adult and Pediatric Adverse Events***

When a single parameter is not appropriate for grading an AE in both adult and pediatric populations, separate parameters with specified age ranges are provided. If there is no distinction between adult and pediatric populations, the listed parameter should be used for grading an AE in both populations.

Determining Severity Grade for Parameters Between Grades

If the severity of an AE could fall under either 1 of 2 grades (eg, the severity of an AE could be either grade 2 or grade 3), sites should select the higher of the 2 grades.

Laboratory normal ranges should be taken into consideration to assign gradings to a laboratory value.

Definitions

Basic self-care functions	Adults : activities such as bathing, dressing, toileting, transfer/movement, continence, and feeding Young children : activities that are age and culturally appropriate (eg, feeding self with culturally appropriate eating implements)
Usual social & functional activities	Activities which adults and children perform on a routine basis and those which are part of regular activities of daily living, for example: Adults : adaptive tasks and desirable activities, such as going to work, shopping, cooking, use of transportation, or pursuing a hobby Young Children : activities that are age and culturally appropriate (eg, social interactions, play activities, learning tasks)
Intervention	Medical, surgical, or other procedures recommended or provided by a healthcare professional for the treatment of an AE.

Estimating Severity Grade for Parameters not Identified in the Grading Table

The functional table below should be used to grade the severity of an AE that is not specifically identified in the grading table. In addition, all deaths related to an AE are to be classified as grade 5.

PARAMETER	GRADE 1 MILD	GRADE 2 MODERATE	GRADE 3 SEVERE	GRADE 4 POTENTIALLY LIFE- THREATENING
Clinical AE NOT identified elsewhere in the grading table	Mild symptoms causing no or minimal interference with usual social & functional activities with intervention not indicated	Moderate symptoms causing greater than minimal interference with usual social & functional activities with intervention indicated	Severe symptoms causing inability to perform usual social & functional activities with intervention or hospitalization indicated	Potentially life-threatening symptoms causing inability to perform basic self-care functions with intervention indicated to prevent permanent impairment, persistent disability, or death

Note: Laboratory abnormalities may have their grading defined in the DAIDS table below, however, all laboratory abnormalities do not necessarily represent an AE. If a laboratory abnormality is considered an AE, the AE need not have the same grade as the laboratory abnormality itself. The AE grade for a laboratory abnormality should be defined by the table above.

MAJOR CLINICAL CONDITIONS				
CARDIOVASCULAR				
PARAMETER	GRADE 1 MILD	GRADE 2 MODERATE	GRADE 3 SEVERE	GRADE 4 POTENTIALLY LIFE- THREATENING
Arrhythmia (by ECG or physical examination) Specify type, if applicable	No symptoms AND No intervention indicated	No symptoms AND Non-urgent intervention indicated	Non-life-threatening symptoms AND Non-urgent intervention indicated	Life-threatening arrhythmia OR Urgent intervention indicated
Blood Pressure Abnormalities^a Hypertension (with the lowest reading taken after repeat testing during a visit) aged ≥18 years	140 to <160 mmHg systolic OR 90 to <100 mmHg diastolic	≥160 to <180 mmHg systolic OR ≥100 to <110 mmHg diastolic	≥180 mmHg systolic OR ≥110 mmHg diastolic	Life-threatening consequences in a participant not previously diagnosed with hypertension (eg, malignant hypertension) OR Hospitalization indicated
aged <18 years	>120/80 mmHg	≥95 th to <99 th percentile + 5 mmHg adjusted for age, height, and gender (systolic and/or diastolic)	≥99 th percentile + 5 mmHg adjusted for age, height, and gender (systolic and/or diastolic)	Life-threatening consequences in a participant not previously diagnosed with hypertension (eg, malignant hypertension) OR Hospitalization indicated
Hypotension	No symptoms	Symptoms corrected with oral fluid replacement	Symptoms AND IV fluids indicated	Shock requiring use of vasopressors or mechanical assistance to maintain blood pressure
Cardiac Ischemia or Infarction Report only 1	NAP	NAP	New symptoms with ischemia (stable angina) OR New testing consistent with ischemia	Unstable angina OR Acute myocardial infarction

ECG: electrocardiogram; IV: intravenous; NAP: not applicable

^a Blood pressure norms for children aged <18 years can be found in: Expert Panel on Integrated Guidelines for Cardiovascular Health and Risk Reduction in Children and Adolescents. *Pediatrics* 2011;128:S213; originally published online November 14, 2011; DOI: 10.1542/peds.2009-2107C.

MAJOR CLINICAL CONDITIONS				
CARDIOVASCULAR				
PARAMETER	GRADE 1 MILD	GRADE 2 MODERATE	GRADE 3 SEVERE	GRADE 4 POTENTIALLY LIFE- THREATENING
Heart Failure	No symptoms AND Laboratory or cardiac imaging abnormalities	Symptoms with mild to moderate activity or exertion	Symptoms at rest or with minimal activity or exertion (eg, hypoxemia) OR Intervention indicated (eg, oxygen)	Life-threatening consequences OR Urgent intervention indicated (eg, vasoactive medications, ventricular assist device, heart transplant)
Hemorrhage (with significant acute blood loss)	NAP	Symptoms AND No transfusion indicated	Symptoms AND Transfusion of ≤ 2 units packed RBCs indicated	Life-threatening hypotension OR Transfusion of > 2 units packed RBCs (for children, packed RBCs > 10 cc/kg) indicated
Prolonged PR Interval or AV Block Report only 1 aged > 16 years	PR interval 0.21 to < 0.25 seconds	PR interval ≥ 0.25 seconds OR Type I 2 nd degree AV block	Type II 2 nd degree AV block OR Ventricular pause ≥ 3.0 seconds	Complete AV block
aged ≤ 16 years	1 st degree AV block (PR interval $>$ normal for age and rate)	Type I 2 nd degree AV block	Type II 2 nd degree AV block OR Ventricular pause ≥ 3.0 seconds	Complete AV block
Prolonged QTc Interval as per Fridericia's formula^b	0.45 to 0.47 seconds	> 0.47 to 0.50 seconds	> 0.50 seconds OR ≥ 0.06 seconds above baseline	Life-threatening consequences (eg, TdP, other associated serious ventricular dysrhythmia)
Thrombosis or Embolism Report only 1	NAP	Symptoms AND No intervention indicated	Symptoms AND Intervention indicated	Life-threatening embolic event (eg, pulmonary embolism, thrombus)

AV: atrioventricular; NAP: not applicable; RBC: red blood cell; TdP: Torsades de Pointes

^b Modified by the sponsor.

DERMATOLOGIC				
PARAMETER	GRADE 1 MILD	GRADE 2 MODERATE	GRADE 3 SEVERE	GRADE 4 POTENTIALLY LIFE- THREATENING
Alopecia (scalp only)	Detectable by participant, representative, or physician AND Causing no or minimal interference with usual social & functional activities	Obvious on visual inspection AND Causing greater than minimal interference with usual social & functional activities	NAP	NAP
Bruising	Localized to 1 area	Localized to more than 1 area	Generalized	NAP
Cellulitis	NAP	Nonparenteral treatment indicated (eg, oral antibiotics, antifungals, antivirals)	IV treatment indicated (eg, IV antibiotics, antifungals, antivirals)	Life-threatening consequences (eg, sepsis, tissue necrosis)
Hyperpigmentation	Slight or localized causing no or minimal interference with usual social & functional activities	Marked or generalized causing greater than minimal interference with usual social & functional activities	NAP	NAP
Hypopigmentation	Slight or localized causing no or minimal interference with usual social & functional activities	Marked or generalized causing greater than minimal interference with usual social & functional activities	NAP	NAP
Petechiae	Localized to 1 area	Localized to more than 1 area	Generalized	NAP
Pruritus^c (without skin lesions)	Itching causing no or minimal interference with usual social & functional activities	Itching causing greater than minimal interference with usual social & functional activities	Itching causing inability to perform usual social & functional activities	NAP
Rash Specify type, if applicable	Localized rash	Diffuse rash OR Target lesions	Diffuse rash AND Vesicles or limited number of bullae OR superficial ulcerations of mucous membrane limited to 1 site	Extensive or generalized bullous lesions OR Ulceration of mucous membrane involving 2 or more distinct mucosal sites OR Stevens-Johnson syndrome OR Toxic epidermal necrolysis

IV: intravenous; NAP: not applicable

^c For pruritus associated with injections or infusions, refer to the [SITE REACTIONS TO INJECTIONS AND INFUSIONS](#) section.

ENDOCRINE AND METABOLIC				
PARAMETER	GRADE 1 MILD	GRADE 2 MODERATE	GRADE 3 SEVERE	GRADE 4 POTENTIALLY LIFE- THREATENING
Diabetes Mellitus	Controlled without medication	Controlled with medication OR Modification of current medication regimen	Uncontrolled despite treatment modification OR Hospitalization for immediate glucose control indicated	Life-threatening consequences (eg, ketoacidosis, hyperosmolar nonketotic coma, end organ failure)
Gynecomastia	Detectable by participant, representative, or physician AND Causing no or minimal interference with usual social & functional activities	Obvious on visual inspection AND Causing pain with greater than minimal interference with usual social & functional activities	Disfiguring changes AND Symptoms requiring intervention or causing inability to perform usual social & functional activities	NAP
Hyperthyroidism	No symptoms AND Abnormal laboratory value	Symptoms causing greater than minimal interference with usual social & functional activities OR Thyroid suppression therapy indicated	Symptoms causing inability to perform usual social & functional activities OR Uncontrolled despite treatment modification	Life-threatening consequences (eg, thyroid storm)
Hypothyroidism	No symptoms AND Abnormal laboratory value	Symptoms causing greater than minimal interference with usual social & functional activities OR Thyroid replacement therapy indicated	Symptoms causing inability to perform usual social & functional activities OR Uncontrolled despite treatment modification	Life-threatening consequences (eg, myxedema coma)
Lipoatrophy^d	Detectable by participant, representative, or physician AND Causing no or minimal interference with usual social & functional activities	Obvious on visual inspection AND Causing greater than minimal interference with usual social & functional activities	Disfiguring changes	NAP
Lipohypertrophy^e	Detectable by participant, representative, or physician AND Causing no or minimal interference with usual social & functional activities	Obvious on visual inspection AND Causing greater than minimal interference with usual social & functional activities	Disfiguring changes	NAP

NAP: not applicable

^d A disorder characterized by fat loss in the face, extremities, and buttocks.

^e A disorder characterized by abnormal fat accumulation on the back of the neck, breasts, and abdomen.

GASTROINTESTINAL				
PARAMETER	GRADE 1 MILD	GRADE 2 MODERATE	GRADE 3 SEVERE	GRADE 4 POTENTIALLY LIFE- THREATENING
Anorexia	Loss of appetite without decreased oral intake	Loss of appetite associated with decreased oral intake without significant weight loss	Loss of appetite associated with significant weight loss	Life-threatening consequences OR Aggressive intervention indicated (eg, tube feeding, total parenteral nutrition)
Ascites	No symptoms	Symptoms AND Intervention indicated (eg, diuretics, therapeutic paracentesis)	Symptoms recur or persist despite intervention	Life-threatening consequences
Bloating or Distension Report only 1	Symptoms causing no or minimal interference with usual social & functional activities	Symptoms causing greater than minimal interference with usual social & functional activities	Symptoms causing inability to perform usual social & functional activities	NAP
Cholecystitis	NAP	Symptoms AND Medical intervention indicated	Radiologic, endoscopic, or operative intervention indicated	Life-threatening consequences (eg, sepsis, perforation)
Constipation	NAP	Persistent constipation requiring regular use of dietary modifications, laxatives, or enemas	Obstipation with manual evacuation indicated	Life-threatening consequences (eg, obstruction)
Diarrhea aged ≥1 year	Transient or intermittent episodes of unformed stools OR Increase of ≤3 stools over baseline per 24-hour period	Persistent episodes of unformed to watery stools OR Increase of 4 to 6 stools over baseline per 24-hour period	Increase of ≥7 stools per 24-hour period OR IV fluid replacement indicated	Life-threatening consequences (eg, hypotensive shock)
aged <1 year	Liquid stools (more unformed than usual) but usual number of stools	Liquid stools with increased number of stools OR Mild dehydration	Liquid stools with moderate dehydration	Life-threatening consequences (eg, liquid stools resulting in severe dehydration, hypotensive shock)
Dysphagia or Odynophagia Report only 1 and specify location	Symptoms but able to eat usual diet	Symptoms causing altered dietary intake with no intervention indicated	Symptoms causing severely altered dietary intake with intervention indicated	Life-threatening reduction in oral intake
Gastrointestinal Bleeding	Not requiring intervention other than iron supplement	Endoscopic intervention indicated	Transfusion indicated	Life-threatening consequences (eg, hypotensive shock)

IV: intravenous; NAP: not applicable

GASTROINTESTINAL				
PARAMETER	GRADE 1 MILD	GRADE 2 MODERATE	GRADE 3 SEVERE	GRADE 4 POTENTIALLY LIFE- THREATENING
Mucositis or Stomatitis Report only 1 and specify location	Mucosal erythema	Patchy pseudomembranes or ulcerations	Confluent pseudomembranes or ulcerations OR Mucosal bleeding with minor trauma	Life-threatening consequences (eg, aspiration, choking) OR Tissue necrosis OR Diffuse spontaneous mucosal bleeding
Nausea	Transient (<24 hours) or intermittent AND No or minimal interference with oral intake	Persistent nausea resulting in decreased oral intake for 24 to 48 hours	Persistent nausea resulting in minimal oral intake for >48 hours OR Rehydration indicated (eg, IV fluids)	Life-threatening consequences (eg, hypotensive shock)
Pancreatitis	NAP	Symptoms with hospitalization not indicated	Symptoms with hospitalization indicated	Life-threatening consequences (eg, circulatory failure, hemorrhage, sepsis)
Perforation (colon or rectum)	NAP	NAP	Intervention indicated	Life-threatening consequences
Proctitis	Rectal discomfort with no intervention indicated	Symptoms causing greater than minimal interference with usual social & functional activities OR Medical intervention indicated	Symptoms causing inability to perform usual social & functional activities OR Operative intervention indicated	Life-threatening consequences (eg, perforation)
Rectal Discharge	Visible discharge	Discharge requiring the use of pads	NAP	NAP
Vomiting	Transient or intermittent AND No or minimal interference with oral intake	Frequent episodes with no or mild dehydration	Persistent vomiting resulting in orthostatic hypotension OR Aggressive rehydration indicated (eg, IV fluids)	Life-threatening consequences (eg, hypotensive shock)

IV: intravenous; NAP: not applicable

MUSCULOSKELETAL				
PARAMETER	GRADE 1 MILD	GRADE 2 MODERATE	GRADE 3 SEVERE	GRADE 4 POTENTIALLY LIFE- THREATENING
Arthralgia	Joint pain causing no or minimal interference with usual social & functional activities	Joint pain causing greater than minimal interference with usual social & functional activities	Joint pain causing inability to perform usual social & functional activities	Disabling joint pain causing inability to perform basic self-care functions
Arthritis	Stiffness or joint swelling causing no or minimal interference with usual social & functional activities	Stiffness or joint swelling causing greater than minimal interference with usual social & functional activities	Stiffness or joint swelling causing inability to perform usual social & functional activities	Disabling joint stiffness or swelling causing inability to perform basic self-care functions
Myalgia (generalized)	Muscle pain causing no or minimal interference with usual social & functional activities	Muscle pain causing greater than minimal interference with usual social & functional activities	Muscle pain causing inability to perform usual social & functional activities	Disabling muscle pain causing inability to perform basic self-care functions
